##### **3.4.1.5 Proportion of patients with at least one COPD exacerbation**

- Number and percentage of patients with at least one COPD exacerbation

- Number and percentage of patients with at least one mild COPD exacerbation
- Number and percentage of patients with at least one moderate COPD exacerbation
- Number and percentage of patients with at least one severe COPD exacerbation
- Number and percentage of patients with at least one moderate or severe COPD exacerbation

#### **3.4.1.6 Time to COPD exacerbation**

- Time to first COPD exacerbation

Time to first COPD exacerbation is calculated by applying the following in the general formula defined in Section 3.1.7.3.

- Event is mild, moderate, or severe COPD exacerbation
- Period refers to the whole study period

For patients who do not experience a COPD exacerbation during the study, start date of the first COPD exacerbation will be censored per general censoring rules described in Section 3.1.2, i.e., the event in question refers to a COPD exacerbation.

- Time to first moderate or severe COPD exacerbation during the first year of treatment

Time to first moderate or severe COPD exacerbation during the first year of treatment is similarly calculated and censored as time to first COPD exacerbation, by considering moderate or severe COPD during the first year of treatment only, i.e., patients will be censored on the date of IP discontinuation or at the end of the first year, whichever is earlier.

- Time to first moderate or severe COPD exacerbation

Time to first moderate or severe COPD exacerbation is similarly calculated and censored as time to first COPD exacerbation, by considering moderate or severe COPD only.

- Time to second COPD exacerbation

Time to second COPD exacerbation is calculated as follows:

*Start Date of the second COPD exacerbation – Date of randomization + 1.*

Time to second COPD exacerbation will be analyzed in patients who experience at least one COPD exacerbation. For patients who experience < 2 COPD exacerbations during the study, start date of the second COPD exacerbation will be censored per general censoring rules described in Section 3.1.2, i.e., the event in question refers to the second COPD exacerbation.

- Time to second moderate or severe COPD exacerbation

Time to second moderate or severe COPD exacerbation is similarly calculated and censored as time to second COPD exacerbation, by considering moderate or severe COPD only.

- Time to third COPD exacerbation

Time to third COPD exacerbation is calculated as follows:

*Start Date of the third COPD exacerbation – Date of randomization + 1.*

Time to third COPD exacerbation will be analyzed in patients who experience at least two COPD exacerbations. For patients who experience < 3 COPD exacerbations during the study, date of the third COPD exacerbation will be censored per general censoring rules described in Section 3.1.2, i.e., the event in question refers to the third COPD exacerbation.

- Time to third moderate or severe COPD exacerbation

Time to third moderate or severe COPD exacerbation is similarly calculated and censored as time to third COPD exacerbation, by considering moderate or severe COPD only.

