#### **4.2.4.3 Additional efficacy variables**

Unless otherwise specified, the following variables will use data collected during the whole study period using on-treatment analysis.

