### **Analyses for COPD Exacerbations**

The rate of COPD exacerbations per patient per year (any, and moderate or severe) and rate of hospitalizations due to COPD exacerbations per patient per year will be analyzed using a Negative Binomial regression model (or Poisson regression model taking overdispersion into account for analyses that Negative Binomial regression does not converge) similar to the primary analysis of the primary efficacy variable. The exposure time will be re-calculated based on the last data collection during the whole study period.

The number of patients with at least one COPD exacerbation (any, mild, moderate, severe, and moderate or severe) will be analyzed based on a logistic regression model with treatment group, baseline ICS use, baseline COPD severity, history of at least one exacerbation in the past year, and smoking status as factors. The estimated treatment effect (i.e., the odds ratio of aclidinium over placebo), corresponding 95% CI, and two-sided p-value for the odds ratio will be presented. The model is as follows:

*Response (Yes=1/No=0) = treatment group + baseline ICS use + baseline COPD severity + history of at least one exacerbation in the past year + smoking status*

Time (in days) to first COPD exacerbation (any, and moderate or severe), time (in days) to second COPD exacerbation (any, and moderate or severe), time (in days) to third COPD exacerbation (any, and moderate or severe), time (in days) to first hospitalization due to COPD exacerbation, and time (in days) to withdrawal of the double-blind IP due to COPD exacerbation will be analyzed by means of Kaplan-Meier estimators and Cox Proportional Hazards model. The estimates of the hazard ratio comparing aclidinium with placebo will be derived using the Cox proportional hazard model for the time in terms of the number of days served as a response variable and treatment group, baseline ICS use, baseline COPD severity, history of at least one exacerbation in the past year, and smoking status as factors. The hazard ratio (aclidinium over placebo), corresponding 95% CI, and two-sided p-value for the hazard ratio will be presented. The model is as follows:

*Survival time = treatment group + baseline ICS use + baseline COPD severity + history of at least one exacerbation in the past year + smoking status*

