In addition, the Kaplan-Meier survival curves will be displayed for each treatment group along with p-value for differences (aclidinium over placebo) based on the Log-Rank test stratified by baseline COPD severity and smoking status.

The durations of COPD exacerbation (any, and moderate or severe; in days) will be summarized descriptively for only the patients who had exacerbations during the treatment period.

Number of days hospitalized due to COPD exacerbations will be summarized for only the patients who had exacerbations during the treatment period. The descriptive statistics of number of days hospitalization due to COPD exacerbations will be summarized by unit type (any, hospitalization unit, intensive care unit, emergency room).

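### Time to second and third exacerbation is analysed only in patients who already had the previous one, so the hazard ratios and p-values are not randomized comparisons

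*SAP*

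**What the plan says.** SAP Section 3.4.1.6 defines the analysis sets: "Time to second COPD exacerbation will be analyzed in patients who experience at least one COPD exacerbation" and "Time to third COPD exacerbation will be analyzed in patients who experience at least two COPD exacerbations". Time is nevertheless counted from randomization: "Start Date of the second COPD exacerbation – Date of randomization + 1". The moderate-or-severe versions are defined by reference: "Time to second moderate or severe COPD exacerbation is similarly calculated and censored as time to second COPD exacerbation". They therefore appear to inherit the restriction, although it is not repeated for them.

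Section 4.2.4.3 sets the data scope, unless otherwise specified: "the following variables will use data collected during the whole study period using on-treatment analysis". It then gives these variables the same Cox model as time to first exacerbation: "The hazard ratio (aclidinium over placebo), corresponding 95% CI, and two-sided p-value for the hazard ratio will be presented". A Kaplan-Meier display adds a p-value "based on the Log-Rank test stratified by baseline COPD severity and smoking status".

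The SAP does not call these subsets non-randomized or limit their output to description. It does not add a version in all patients, although Section 4.2.4 places all efficacy analyses in the FAS.

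**The concern.** Having had a first or second exacerbation is an outcome. Aclidinium is expected to make it rarer, and in an on-treatment analysis it also depends on how long the patient stayed on IP. Selecting on it gives two groups that differ for reasons other than chance at randomization.

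The mechanism is simple. Every second exacerbation occurs in someone who had a first, so the restriction loses no events. It removes only patients who could never contribute an event, together with their event-free time. If the drug works, more such patients are removed from the aclidinium arm, and the hazard ratio moves toward 1. If discontinuation differs between arms, more are removed from the arm with shorter exposure, whose hazard then looks too high. That can produce a false benefit or a false harm with no drug effect at all.

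The SAP itself allows for unequal discontinuation. Section 4.2.1 compares time to IP discontinuation between arms by log-rank test, and withdrawal because of an exacerbation is an efficacy variable: "time (in days) to withdrawal of the double-blind IP due to COPD exacerbation will be analyzed by means of Kaplan-Meier estimators".

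At stake are four endpoints: second and third, any severity and moderate or severe. Their p-values would be read as randomized evidence.

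**Working it through.** **Inputs.** From SAP Section 1.3.2: 4,000 patients, placebo rate 0.8 per patient-year, rate ratio 0.86, k = 0.67, 30% discontinuation in year 1. From Section 1.2: 1:1 allocation (2,000 per arm). From Section 3.4.1: maximum follow-up about 36 months. From Section 4.1: two-sided 0.05.

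**Reproducing the SAP's own figure.** The SAP gives no power for the second or third event, but the same inputs underlie its roughly 89% power for the exacerbation rate.
- Mean first-year exposure, exponential discontinuation: 0.30 / (−ln 0.70) = 0.841 years.
- Variance of the log rate ratio = Σ over arms of (1/(tλ) + k)/n = (1/(0.841 × 0.8) + 0.67)/2000 + (1/(0.841 × 0.688) + 0.67)/2000 = 0.00228, so SE = 0.0477.
- Power = Φ(|ln 0.86|/0.0477 − 1.96) = Φ(1.20) = 88.5%, which agrees with the stated figure.

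**Simulation.** Exacerbations follow a Poisson process with gamma frailty of variance 0.67. IP discontinuation is exponential and independent of exacerbations. Follow-up stops at 36 months. An unadjusted Cox model on treatment was fitted to the same 1,500 simulated trials twice: in all patients, and in those with the prior event before censoring. Monte Carlo error is about 1.3 percentage points or less.

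*Effect present (rate ratio 0.86), 30% first-year discontinuation in both arms, moderate or severe:*

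| | In subset, placebo / aclidinium | HR, all FAS | HR, subset | Power, all FAS | Power, subset |
|---|---|---|---|---|---|
| Second | 56.5% / 53.2% | 0.85 | 0.89 | 85% | 58% |
| Third | 34.1% / 30.3% | 0.81 | 0.88 | 86% | 40% |

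For the second event the restriction removes 100 − 53.2 = 46.8% of aclidinium patients but 100 − 56.5 = 43.5% of placebo patients.

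**Hand check of the power loss.** Events are the same in both analyses: about 1,287 second and 775 third. With SE ≈ 2/√events and power = Φ(|ln HR|/SE − 1.96), using three-decimal hazard ratios from a separate simulation:
- Second: SE = 0.0557. HR 0.846 gives Φ(1.04) = 85%; HR 0.887 gives Φ(0.19) = 58%.
- Third: SE = 0.0718. HR 0.807 gives Φ(1.02) = 85%; HR 0.886 gives Φ(−0.28) = 39%.

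The whole loss comes from the shifted estimate, none from lost precision.

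**Other discontinuation input.** With 40% discontinuation at two years (Section 1.3.1), power falls from 88% to 62% (second) and from 90% to 44% (third). A separate 600-trial run gave 65% and 46% in the subset.

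**Any severity.** The SAP gives no rate, so a range was assumed:

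| Assumed rate per year | Second, all FAS → subset | Third, all FAS → subset |
|---|---|---|
| 1.0 | 88% → 66% | 89% → 49% |
| 1.2 | 89% → 69% | 91% → 55% |
| 2.0 | 90% → 76% | 93% → 67% |

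**No drug effect, 0.8 per year:**

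| Discontinuation per year, placebo / aclidinium | Subset HR, second / third | Subset rejection, second / third |
|---|---|---|
| 30% / 30% | 1.00 / 0.995 | 6.3% / 5.0% |
| 35% / 25% (assumed) | 0.96 / 0.95 | 10.5% / 13.9% |
| 25% / 35% (assumed) | 1.05 / 1.06 | 12.7% / 12.2% |

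In the two unequal cases almost all rejections favour the arm with less discontinuation. Analysing all FAS patients gives HR 1.00 and 5 to 6% rejection in both.

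**The case against.** **Who enters the subset is not fully fixed.** Section 3.4.1 says its variables use data from the whole study period, which Section 1.2 defines as on plus off treatment. If the prior event may also occur after IP discontinuation, most of the false-positive inflation disappears. At 35% / 25% discontinuation, rejection was 4.7% and 6.8% if half of the discontinuers leave the study, and 3.7% and 5.5% if none do. This stands as a limit on the false-positive figures. It does not rescue the rule: Section 4.2.4.3 makes these on-treatment analyses, and under the whole-study reading power still falls, to 58% and 46%.

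**The discontinuation gap is assumed.** The SAP gives no rates by arm. At 32% versus 28%, rejection was 6.7% and 6.0%, against 5.7% and 6.3% in all FAS, which is no material inflation. This stands too: a false signal needs a large gap. With equal discontinuation the tests keep their level.

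**The largest losses are for moderate-or-severe events**, where the restriction is inferred. For any severity, where it is explicit, the loss is smaller at the assumed rates, but still substantial.

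**Part of the difference is a difference of estimand.** For the third event the all-FAS hazard ratio (0.81) lies further from the input rate ratio of 0.86 than the subset value (0.88). That is correct: the gap is not all error around a common target. But only the all-FAS value compares randomized groups.

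**The simulation is simplified.** It omits covariates and the 7-day rule and gives everyone 36 months. The planned covariates should absorb some of the frailty that drives selection; by how much was not assessed.

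**These endpoints are additional**, outside the testing sequence. That limits the consequences, but does not make the estimate a randomized one.

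**Conclusion.** The concern holds. The SAP restricts these analyses by a post-randomization outcome and reports them as treatment comparisons. At its own moderate-or-severe inputs the hazard ratio moves toward 1 by about 0.04 (second) and 0.07 (third), costing 27 and 46 percentage points of power (85 − 58; 86 − 40). That attenuation persists under either reading of who enters the subset. It rests on gamma frailty, discontinuation independent of exacerbations, and an unadjusted model.

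The risk of a false benefit or harm is real but conditional. It requires the on-treatment reading of membership and a gap in discontinuation as large as the assumed 35% versus 25% per year.

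The plan should be changed. The primary and secondary efficacy conclusions and the MACE conclusion do not depend on it.

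**What to change.** In SAP Section 3.4.1.6, delete the two sentences that restrict the analysis sets. Analyse time from randomization to the second and to the third exacerbation in all FAS patients. The existing censoring sentences for patients with fewer than two or fewer than three exacerbations already cover patients with none, under Section 3.1.2. Add one line stating that the moderate-or-severe versions follow the same rule.

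If time from one exacerbation to the next in patients with a prior event is of interest, present it as descriptive, without a p-value, because it remains a selected comparison.

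The cost is two sentences deleted, one added, and a subset filter removed from the programs. No new data are needed.

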#### **3.4.1.7 Time to Withdrawal from the double-blind IP due to COPD exacerbation**

Time (in days) to withdrawal from the double-blind IP due to COPD exacerbation is calculated as follows:

*Date of withdrawal from the double-blind IP due to COPD exacerbation – Date of randomization + 1.*

- For patients who do not withdraw from the double-blind IP, date of withdrawal from the double-blind IP due to COPD exacerbation will be censored at the last dose date.
- For patients who withdraw from the double-blind IP due to reasons other than COPD exacerbation, patients will be censored at the date of withdrawal from the double-blind IP (due to reasons other than COPD exacerbation).

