## **1.3 Number of subjects**

### **1.3.1 Power for the primary safety endpoint: time to first MACE event**

For this study, a total of 122 patients with MACE will be needed to have 90% power, at 5% significance level, to rule out a hazard ratio of 1.8 in time to first MACE in acclidinium bromide treated patients relative to placebo, assuming the hazard rate is 1.0 under the alternative hypothesis. The justification for the hazard ratio of margin of 1.8 is provided in Appendix IV of the CSP.

This ASCENT COPD study will be recruiting patients with a FEV1 below 80% and a planned maximum of 36 months double-blind treatment period. The assumption of 1.9 MACE per 100 patient years would be reasonable for this study (See Section 9.7.9.1 of the CSP for details). To obtain 122 MACE in this study with 1.9 MACE per 100 patient years of treatment, a total of 6,500 patient years of treatment (aclidinium bromide and placebo) would be needed. Assuming a treatment discontinuation rate of 40% and a study discontinuation rate of 20% at year 2, and following an exponential distributions for time to events and time to discontinuations, a sample size of 4000 is needed to ensure 90% power to observe 122 events applying the on-study analysis, and an 80% power to observe 91 events applying the on-treatment analysis.

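### Kaplan-Meier curves for time to IP withdrawal due to COPD exacerbation censor withdrawals for other reasons and deaths, so they overstate each arm's probability of this withdrawal; the hazard ratio and log-rank test are unaffected

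*SAP*

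**What the plan says.** SAP Section 3.4.1.7 defines the time as "Date of withdrawal from the double-blind IP due to COPD exacerbation – Date of randomization + 1". It then sets two censoring rules:

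- For patients who do not withdraw from IP, the "date of withdrawal from the double-blind IP due to COPD exacerbation will be censored at the last dose date".
- For other withdrawals: "For patients who withdraw from the double-blind IP due to reasons other than COPD exacerbation, patients will be censored at the date of withdrawal".

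Section 3.1.2 adds a general rule that deaths censor any endpoint of which death is not a part.

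Under Analyses for COPD Exacerbations in Section 4.2.4.3, "withdrawal of the double-blind IP due to COPD exacerbation will be analyzed by means of Kaplan-Meier estimators and Cox Proportional Hazards model". The same section says that "the Kaplan-Meier survival curves will be displayed for each treatment group along with p-value for differences" from a log-rank test stratified by baseline COPD severity and smoking status. The SAP plans no cumulative incidence estimate for this endpoint.

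On how common stopping is expected to be, Section 1.3.1 plans as follows: "Assuming a treatment discontinuation rate of 40% and a study discontinuation rate of 20% at year 2", with exponential times. Section 1.3.2 assumes 30% treatment discontinuation in the first year for the efficacy power.

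**The concern.** Kaplan-Meier treats a censored patient as someone who could still have the event later, at the same rate as those who remain. That is untenable here. Once a patient has stopped IP for another reason, or has died, withdrawal from IP because of an exacerbation is impossible by definition. The exacerbation endpoints in Section 3.4.1.6 are different, because an exacerbation can still happen after IP stops and is collected in post-treatment follow-up.

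One minus the Kaplan-Meier estimate therefore describes a hypothetical trial in which nobody stops IP for any other reason. It is higher than the proportion who actually withdraw because of an exacerbation whenever other withdrawals occur, and the SAP's planning figures make those common. The report would show arm curves that do not fit the percentages by reason in the disposition tables of Section 4.2.1.

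**Working it through.** The SAP states no figure for this endpoint, so there is nothing to reproduce. The check sizes the gap from the SAP's own discontinuation assumption.

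**Inputs**

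- All-reason IP discontinuation D = 40% at T = 2 years, exponential (Section 1.3.1).
- Maximum follow-up about 36 months (Section 3.4.1).
- Share s of discontinuations due to COPD exacerbation: not in the SAP; assumed 5%, 10% and 20%.

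**Formulas**, with constant cause-specific hazards:

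- All-reason hazard: λ = −ln(1 − 0.40)/2 = 0.2554 per year.
- What Kaplan-Meier estimates when other reasons are censored: 1 − exp(−sλT).
- Actual cumulative incidence: s × (1 − exp(−λT)) = s × D(T).

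**Year 2** (D = 40%, λT = 0.5108)

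| Share s | 1 − KM | Actual | Gap (points) | Ratio |
|---|---|---|---|---|
| 5% | 2.52% | 2.00% | 0.5 | 1.26 |
| 10% | 4.98% | 4.00% | 1.0 | 1.25 |
| 20% | 9.71% | 8.00% | 1.7 | 1.21 |

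**36 months**, extending the year-2 hazard (D = 1 − exp(−3 × 0.2554) = 53.5%)

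| Share s | 1 − KM | Actual | Gap (points) | Ratio |
|---|---|---|---|---|
| 5% | 3.76% | 2.68% | 1.1 | 1.40 |
| 10% | 7.38% | 5.35% | 2.0 | 1.38 |
| 20% | 14.21% | 10.70% | 3.5 | 1.33 |

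A simulation of 400,000 patients over 3 years agreed: 7.5% against 5.4% at s = 10%, and 14.2% against 10.7% at s = 20%.

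**Year 1**, using the 30% of Section 1.3.2 instead: 1.8% against 1.5%, 3.5% against 3.0%, and 6.9% against 6.0% for the same three shares. The two planning figures do not lie on one exponential curve (0.2554 per year gives 1 − exp(−0.2554) = 22.5% at year 1), so each is used at its own time point.

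**Internal consistency.** Take s = 10% at year 2. The Kaplan-Meier complement is 4.98% for exacerbation and 1 − exp(−0.9 × 0.5108) = 36.9% for all other reasons. These add to 41.8%, although only 40% have stopped. Cumulative incidences (4% and 36%) add up correctly. Section 4.2.1 also plots all-reason discontinuation by Kaplan-Meier. At 36 months a reader comparing that curve (53.5%) with this one (7.4%) would put the exacerbation share at 7.38/53.5 = 13.8%, when the true share is 10%.

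**The case against.** The case for leaving the plan alone has several parts.

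- **Low stakes.** This is an additional efficacy variable. The sequential testing in Section 4.2.4 covers only the primary and secondary efficacy endpoints. This stands.
- **The comparisons are sound.** With other reasons censored, the Cox hazard ratio and the log-rank test compare cause-specific hazards. This stands. A reader might infer that the hazard ratio or p-value is biased; the overstatement of the arm curves does not imply that.
- **Percentages by reason appear elsewhere.** Section 4.2.1 tabulates discontinuation by reason and arm, overall and for the first year, and plots time against reason. This softens the harm, but crude percentages do not replace a curve over time, and the Kaplan-Meier curve will disagree with them.
- **Censoring at IP discontinuation is the SAP's on-treatment rule.** That explains the wording. It does not justify it for an endpoint in which IP discontinuation is itself the event.
- **The sizes rest on assumptions.** The share is assumed, and the 36-month figures extrapolate beyond year 2. This stands for the size but not the direction.

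A reader might also infer that the Kaplan-Meier curves hide a real difference between arms. Suppose equal exacerbation-withdrawal hazards of 0.0255 per year, and all-reason discontinuation at year 2 of 45% on placebo and 35% on aclidinium. At 36 months Kaplan-Meier shows 7.4% in both arms, while the cumulative incidences are 5.1% and 5.6%. The equal curves correctly reflect equal hazards; the incidences differ because patients who stay on IP longer remain at risk longer. The two estimators answer different questions. Nothing in the SAP says that discontinuation is expected to differ by arm.

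**Conclusion.** The point holds for the arm-level probabilities and curves of this one endpoint. Other-reason withdrawal and death rule out the event, yet both are censored and the result is reported by Kaplan-Meier, so the probability of withdrawal due to exacerbation is overstated in each arm.

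The upward direction follows whenever any such withdrawals occur and does not depend on the share. The size does: the ranges of 0.5 to 1.7 points at year 2 and 1.1 to 3.5 points at 36 months assume shares of 5% to 20% and constant hazards, and the second range also assumes that the year-2 hazard continues.

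No primary or secondary conclusion changes. It is a modest correction, worth making because it is cheap and removes a known bias.

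**What to change.** In Section 3.4.1.7, state that when arm-level probabilities are estimated, IP withdrawal for any other reason and death on IP are competing events. In Section 4.2.4.3, for this endpoint, report Aalen-Johansen cumulative incidence curves by arm with 95% CIs in place of the Kaplan-Meier curves, or at minimum beside them with a note on what each one estimates.

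Keep the planned Cox model and stratified log-rank test, with other reasons censored as now, and label both cause-specific. Gray's test is not needed: it compares subdistributions, and its p-value would sit beside a cause-specific hazard ratio that answers a different question.

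The cost is a few lines of SAP text and one extra analysis step. Reasons for stopping IP are already recorded on the eCRF and Section 3.4.1.7 already uses the withdrawal dates, so no new data are needed. The reported probabilities will be lower than the Kaplan-Meier ones.
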